5.3 Life-threatening (21 CFR 312.32(a))	

## **1.0 PROTOCOL SYNOPSIS**

Title	Phase I/IIa gene transfer clinical trial for Duchenne Muscular Dystrophy using rAAVrh74.MCK.GALGT2
Study Number	Cohort 1: N = 1 [Low dose: 2.5 x $10^{13}$ vg/kg per leg, delivered bilaterally (total 5.0 x $10^{13}$ vg/kg)]
	Cohort 2: N=1 [High dose: 5x10  vg/kg per leg, delivered bilaterally (total 1.0 x 10  vg/kg)]
Clinical Study Phase	Phase I/IIa trial
Number of Centers	Single site (Nationwide Children's Hospital)
Study Objectives	The primary objective is assessment of safety.
Study Design	Dose escalation study rAAVrh74.MCK.GALGT2:
g	- Intravascular limb infusion for gene transfer delivered bilaterally (two cohorts) via a major lower limb artery to the whole lower limb of DMD subjects.
Patient Population	Inclusion Criteria
	• Ambulant patients age 4 years or older
	• Confirmed mutations in the DMD gene using a clinical accepted technique that completely defines the mutation
	
 
Measurably impaired muscle function (defined as less than 80% of the predicted value for age 100 MWT), but with sufficient muscle preservation to ensure assessment of muscle transfection based on clinical evaluation by the PI and expert colleagues. This degree of preservation will include:         
 
Ability to extend the knee fully against gravity
 
Preserved ambulation with ability to walk ≥ 350 meters
 
 
 

	
 
a magnetic resonance image of the quadriceps showing preservation of sufficient muscle mass to permit transfection
 

	• Males of any ethnic group will be eligible
	
 
Ability to cooperate with muscle testing
 
Stable dose of corticosteroid therapy (including either prednisone, prednisolone, deflazacort or their generic forms) for at least 12 weeks prior to gene transfer
 

	Exclusion Criteria
	• Active viral infection based on clinical observations
	• The presence of a DMD mutation without weakness or loss of function
	• Subject is amenable to or is currently being treated with eteplirsen
	
 
Symptoms or signs of cardiomyopathy, including:
 

	
 
Dyspnea on exertion, pedal edema, shortness of breath upon lying flat, or rales at the base of the lungs
 


 
Serological evidence of HIV infection, or Hepatitis B or C infecti         
 
Diagnosis of (or ongoing treatment for) an autoimmune disease
 
Persistent leukopenia or leukocytosis (WBC ≤ 3.5 K/µL or ≥ 20.0 K/µL) or an absolute neutrophil count < 1.5K/µL
 
Concomitant illness or requirement for chronic drug treatment the in the opinion of the PI creates unnecessary risks for gene transfer
 
Subjects with rAAVth74 binding antibody titers ≥ 1:50 as determined by ELISA immunoassay
 
Presence of circulating anti-Sda antibodies as determined by study approved laboratory values in the clinically significant range, based upon normal values in the Nationwide Children's Hospital Laboratory
 
Abnormal laboratory values in the clinically significant range, based upon normal values in the Nationwide Children's Hospital Laboratory
 
The vector will be delivered by intravascular limb infusion (ILI-GT) to the vector will be delivered by intravascular limb infusion (ILI-GT) to the vector will be delivered by intravascular limb infusion (ILI-GT) to the vector will be delivered by intravascular limb infusion (ILI-GT) to the vector will be delivered by intravascular limb. Study subjects will receive general anesthesia during the procedure following Children's Hospital protocol.
 
Detailed description of vector administration procedures can be found in section 3.6.3 of this clinical protocol.
 
Detailed description of vector administration procedures can be found in section as 0.6 and 180 days post-injection
 
GALGT2 protein expression quantified by western blot and assessed by densitometry in muscle biopsy tissue at 90 and 180 days post-injection
 
GALGT2 protein expression quantified by western blot and assessed by densitometry in muscle biopsy tissue at 90 and 180 days post-injection
 
GALGT2

		
GT) to       each lower limb. Study subjects will receive general anesthesia during the procedure following Children's Hospital protocol.         Primary Outcome       Safety is a primary outcome for this clinical protocol.         Secondary       We propose the following efficacy outcome measures in leg muscles, eac in comparison to baseline values:         • Expression of GALGT2 as demonstrated by immunofluorescent staining with anti-CT epitope antibodies or WFA lectin in muscle biopsy sections at 90 and 180 days post-injection         • GALGT2 protein expression quantified by western blot and assessed by densitometry in muscle biopsy tissue at 90 and 180 days post-injection         • We propose the following exploratory clinical outcome measures, each in comparison to baseline values:         • The 6 minute walk test (6MWT), with either stabilization or a statistically significant change in distance walked on the 6MWT a 90 and 180 days after injection to be considered evidence of a positive result.         • Strength and functional testing will be performed at baseline and days 90,180, and at months 12, 18 and 24. The maximum voluntat isometric contraction testing (MVICT), which will provide the force generated by the muscles of knee extension and knee flexion will be an exploratory measure, as will the 100 meter walk time a		
 
Persistent leukopenia or leukocytosis (WBC ≤ 3.5 K/µL or ≥ 20.0 K/µL) or an absolute neutrophil count < 1.5K/µL
 
Concomitant illness or requirement for chronic drug treatment that in the opinion of the PI creates unnecessary risks for gene transfer
 
Subjects with rAAVrh74 binding antibody titers ≥ 1:50 as determined by ELISA immunoassay
 
Presence of circulating anti-Sda antibodies as determined by study approved laboratory
 
Abnormal laboratory values in the clinically significant range, based upon normal values in the Nationwide Children's Hospital Laboratory
 

Children's Hospital protocol.• Detailed description of vector administration procedures can be found in section 3.6.3 of this clinical protocol.Primary OutcomeSafety is a primary outcome for this clinical gene transfer trial.Secondary OutcomesWe propose the following efficacy outcome measures in leg muscles, eac in comparison to baseline values:• Expression of GALGT2 as demonstrated by immunofluorescent staining with anti-CT epitope antibodies or WFA lectin in muscle biopsy sections at 90 and 180 days post-injection• GALGT2 protein expression quantified by western blot and assessed by densitometry in muscle biopsy tissue at 90 and 180 days post-injectionWe propose the following exploratory clinical outcome measures, each in comparison to baseline values:• The 6 minute walk test (6MWT), with either stabilization or a statistically significant change in distance walked on the 6MWT a 90 and 180 days 90, 180, and at months 12, 18 and 24. The maximum volunta isometric contraction testing (MVICT), which will provide the force generated by the muscles of knee extension and knee flexion will be an exploratory measure, as will the 100 meter walk time at	Study Procedures	GT) to each lower limb. Study subjects will

 
Detailed description of vector administration procedures can be found in section 3.6.3 of this clinical protocol.
 
Primary Outcome
 
Safety is a primary outcome for this clinical gene transfer trial.
 
Secondary
 
Outcomes
 
We propose the following efficacy outcome measures in leg muscles, eac in comparison to baseline values:         
 
Expression of GALGT2 as demonstrated by immunofluorescent staining with anti-CT epitope antibodies or WFA lectin in muscle biopsy sections at 90 and 180 days post-injection
 
GALGT2 protein expression quantified by western blot and assessed by densitometry in muscle biopsy tissue at 90 and 180 days post-injection
 
 
 
We propose the following exploratory clinical outcome measures, each in comparison to baseline values:         
 
The 6 minute walk test (6MWT), with either stabilization or a statistically significant change in distance walked on the 6MWT a 90 and 180 days after injection to be considered evidence of a positive result.
 
Strength and functional testing will be performed at baseline and days 90,180, and at months 12, 18 and 24. The maximum volunta isometric contraction testing (MVICT), which will provide the force generated by the muscles of knee extension and knee flexion will be an exploratory measure, as will the 100 meter walk time at the set of th

		
found in section 3.6.3 of this clinical protocol.Primary OutcomeSafety is a primary outcome for this clinical gene transfer trial.Secondary OutcomesWe propose the following efficacy outcome measures in leg muscles, eac in comparison to baseline values:•Expression of GALGT2 as demonstrated by immunofluorescent staining with anti-CT epitope antibodies or WFA lectin in muscle biopsy sections at 90 and 180 days post-injection•GALGT2 protein expression quantified by western blot and assessed by densitometry in muscle biopsy tissue at 90 and 180 days post-injectionWe propose the following exploratory clinical outcome measures, each in comparison to baseline values:•The 6 minute walk test (6MWT), with either stabilization or a statistically significant change in distance walked on the 6MWT a 90 and 180 days after injection to be considered evidence of a positive result.•Strength and functional testing will be performed at baseline and days 90,180, and at months 12, 18 and 24. The maximum volunta isometric contraction testing (MVICT), which will provide the force generated by the muscles of knee extension and knee flexion will be an exploratory measure, as will the 100 meter walk time a		
Primary OutcomeSafety is a primary outcome for this clinical gene transfer trial.Secondary OutcomesWe propose the following efficacy outcome measures in leg muscles, each in comparison to baseline values:•Expression of GALGT2 as demonstrated by immunofluorescent staining with anti-CT epitope antibodies or WFA lectin in muscle biopsy sections at 90 and 180 days post-injection•GALGT2 protein expression quantified by western blot and assessed by densitometry in muscle biopsy tissue at 90 and 180 days post-injection•We propose the following exploratory clinical outcome measures, each in comparison to baseline values:•The 6 minute walk test (6MWT), with either stabilization or a statistically significant change in distance walked on the 6MWT a 90 and 180 days after injection to be considered evidence of a positive result.•Strength and functional testing will be performed at baseline and days 90,180, and at months 12, 18 and 24. The maximum volunta isometric contraction testing (MVICT), which will provide the force generated by the muscles of knee extension and knee flexion will be an exploratory measure, as will the 100 meter walk time at		

 
Secondary Outcomes
 
We propose the following efficacy outcome measures in leg muscles, each in comparison to baseline values: 
 
Expression of GALGT2 as demonstrated by immunofluorescent staining with anti-CT epitope antibodies or WFA lectin in muscle biopsy sections at 90 and 180 days post-injection
 
GALGT2 protein expression quantified by western blot and assessed by densitometry in muscle biopsy tissue at 90 and 180 days post-injection
 
We propose the following exploratory clinical outcome measures, each in comparison to baseline values:
 
The 6 minute walk test (6MWT), with either stabilization or a statistically significant change in distance walked on the 6MWT a 90 and 180 days after injection to be considered evidence of a positive result.
 
Strength and functional testing will be performed at baseline and days 90,180, and at months 12, 18 and 24. The maximum volunta isometric contraction testing (MVICT), which will provide the force generated by the muscles of knee extension and knee flexion will be an exploratory measure, as will the 100 meter walk time at the strength of the state of the strength and strength or the strength of the strength or the s

	Primary Outcome	

 
Outcomes
 
in comparison to baseline values: 
 
Expression of GALGT2 as demonstrated by immunofluorescent staining with anti-CT epitope antibodies or WFA lectin in muscle biopsy sections at 90 and 180 days post-injection
 
GALGT2 protein expression quantified by western blot and assessed by densitometry in muscle biopsy tissue at 90 and 180 days post-injection
 
 
 
We propose the following exploratory clinical outcome measures, each in comparison to baseline values: 
 
The 6 minute walk test (6MWT), with either stabilization or a statistically significant change in distance walked on the 6MWT a 90 and 180 days after injection to be considered evidence of a positive result.
 
Strength and functional testing will be performed at baseline and days 90,180, and at months 12, 18 and 24. The maximum volunta isometric contraction testing (MVICT), which will provide the force generated by the muscles of knee extension and knee flexion will be an exploratory measure, as will the 100 meter walk time at the strength and st

	Contrast Con	

 
Expression of GALGT2 as demonstrated by immunofluorescent staining with anti-CT epitope antibodies or WFA lectin in muscle biopsy sections at 90 and 180 days post-injection
 
GALGT2 protein expression quantified by western blot and assessed by densitometry in muscle biopsy tissue at 90 and 180 days post-injection
 
We propose the following exploratory clinical outcome measures, each in comparison to baseline values:         
 
The 6 minute walk test (6MWT), with either stabilization or a statistically significant change in distance walked on the 6MWT a 90 and 180 days after injection to be considered evidence of a positive result.
 
Strength and functional testing will be performed at baseline and days 90,180, and at months 12, 18 and 24. The maximum volunta isometric contraction testing (MVICT), which will provide the force generated by the muscles of knee extension and knee flexion will be an exploratory measure, as will the 100 meter walk time at the strengt and strengt an

	-	

 
comparison to baseline values:
 
The 6 minute walk test (6MWT), with either stabilization or a statistically significant change in distance walked on the 6MWT a 90 and 180 days after injection to be considered evidence of a positive result.
 
Strength and functional testing will be performed at baseline and a days 90,180, and at months 12, 18 and 24. The maximum volunta isometric contraction testing (MVICT), which will provide the force generated by the muscles of knee extension and knee flexion will be an exploratory measure, as will the 100 meter walk time at the statement of the statem

		
 
staining with anti-CT epitope antibodies or WFA lectin in muscle biopsy sections at 90 and 180 days post-injection
 
GALGT2 protein expression quantified by western blot and assessed by densitometry in muscle biopsy tissue at 90 and 180
 

	Cohort 2: N=1 [High dose: 5x10  vg/kg per leg, delivered bilaterally (total 1.0 x 10  vg/kg)]
Statistical Analysis	This is a phase I/IIa trial, with safety as the primary measure.
	Quantification of the number of fibers expressing GALTG2 as determined by quantification of the number of fibers and the intensity of anti-CT antibody or WFA lectin staining at the sarcolemma based on quantitative image analysis will be analyzed using a paired t-test.
	The 6MWT will be the leading exploratory efficacy measure (secondary outcome).
	Strength measures, an exploratory outcome, will also be performed by the 100 meter walk/run and MVICT of limb muscles and analyzed by paired t-tests with a significance level of $p = 0.05$ .
	For each of these measures, statistical analysis based on differences between pre- and post-gene transfer examinations will be analyzed using a paired t-test, with a p value of $< 0.05$ indicating significance.
Long-term follow-up	We will follow the most recent FDA guidance with regard to long-term subject follow up post gene transfer. As indicated by the guidelines, our proposed vector has a very low probability of gene transfer-related delayed adverse events. We will, however, evaluate short-term safety over a two- year period that incorporates the active phase of the protocol.

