#### 2.1 Abstract

The proposed clinical trial is a dose escalation study of rAAVrh74.MCK.GALGT2 for DMD patients. There will be a modified intravascular limb infusion(ILI);

 henceforth designated as intravascular limb infusion for gene therapy (ILI-GT) delivered sequentially to the whole each lower limb of DMD subjects via a major lower limb artery.

ILI-GT will be delivered to the muscles of both legs of DMD subjects. This approach to vascular gene transfer builds upon previously published methods used in mice and non-human primates.

Two cohorts will undergo gene transfer in a standard dose escalation scheme to establish maximum tolerated dose (MTD) using toxicity. One subject will be enrolled into the first cohort and one subject will be enrolled in the second cohort. The first cohort will receive the minimally efficacious dose as established by primate studies, consisting of  $2.5 \times 10^{13}$  vg/kg per leg, delivered bilaterally (to total  $5.0 \times 10^{13}$  vg/kg per subject). Once safety is established in the low-dose cohort, the second cohort will receive  $5 \times 10^{13}$  vg/kg per leg, delivered bilaterally (to total  $1.0 \times 10^{14}$  vg/kg per subject).

The baseline open muscle biopsy will be performed in one quadriceps muscle. Open muscle biopsy of the quadriceps (in the leg contralateral to the pre-treatment biopsy) will be performed at 90 days post ILI-GT procedure.

Every effort

will be made to sample these same muscles in all patients; however, in subjects (particularly older ambulant subjects) with limited quadriceps musculature, alternate muscle biopsy sites may be selected at the PIs discretion (including gastrocnemius or tibialis anterior muscles).

The primary objective of this study is the assessment of the safety of intravascular administration of rAAVrh74.MCK.GALGT2 to DMD patients. Safety endpoints will be assessed by changes in hematology, serum chemistry, urinalysis, immunologic response to

rAAVrh74 and GALGT2, and reported history and observations of symptoms. Efficacy measures will be used as secondary outcome for this disorder including a combination of functional 6 minute walk test (6MWT) and direct muscle testing for strength (MVICT) of lower limb muscles.

Subjects will be evaluated at baseline, infusion visit (days 0-2), and return for follow up visits on days 7, 14, 30, 60, 90, and 180 and months 12, 18 and 24.

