#### 3.6 Gene Transfer Protocol

#### 3.6.1 Baseline Measures Prior to Vector Injection (Day -45 to Day -1)

Informed consent will be obtained prior to the collection of any data and any study related procedures. Baseline measures from subjects will be obtained prior to gene transfer. A complete physical examination, medical history and concomitant medication history will be obtained. Vitals will be obtained, including temperature, respiratory rate, heart rate, blood pressure, height, and weight. Pre-treatment studies will also include

echocardiogram, ECG, the North Star Ambulatory Assessment (NSAA), a video recorded six minute walk test (6MWT), the 100 meter walk/run test, the maximum voluntary isometric contraction testing (MVICT) of knee extension and knee flexors bilaterally, pulmonary function testing (PFTs) including spirometry, and an open muscle biopsy.

Lab work will include the following:

- Complete blood cell count (CBC) and differential, platelets
- Aspartate aminotransferase (AST)/alanine transaminase (ALT)
- Gamma-glutamyl transpeptidase (GGT)\*
- A Comprehensive Metabolic Panel (CMP) that includes:
  - Albumin/Serum total protein
  - Serum total bilirubin
  - Electrolytes
  - o Calcium
  - Creatinine/Blood Urea Nitrogen (BUN)
  - Serum glucose
  - Alkaline phosphatase
- Prothrombin time (PT)/activated partial thromboplastin time (PTT)
- Amylase
- Creatine kinase (CK)
- Cystatin C
- Antibody testing for Hepatitis B,C and HIV1 and 2.
- Urinalysis
- Whole blood for biobanking
- Urine for biobanking

\* For subjects taking drugs that potentially induce GGT synthesis through the cytochrome P450 system, the clinically significant range will be estimated at two times the levels obtained from the baseline screening test.

Additionally, ELISA will be performed for detection of total antibodies to AAVrh74 and anti-Sda, and ELISpots for T-cell responses to AAVrh74 and GALGT2.

A baseline open muscle biopsy will be performed in one quadriceps muscle. (Note that the rationale and methods of muscle biopsy site selection and performance for this and subsequent biopsies are discussed in Section 3.8)

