#### 3.8 Muscle biopsy

The baseline open muscle biopsy will be performed in one quadriceps muscle, or other appropriate muscle as determined by the PI. Open muscle biopsy of the quadriceps, or other muscle as determined by the PI (biopsy will be in the contralateral leg to the pre-treatment biopsy, unless otherwise determined by the PI), will be performed at 3 months post-infusion.

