			ges to the stud er multiple da	dy, parents will be r	e-conse	nted at th	neir next v	isit.										
					) and vis	its 8-10 v	vill be per	formed at	least 1 da	y precedi	ng the bio	psy.						
	
 
Muscle strength testing at baseline (days -45 to -1) and visits 8-10 will be performed at least 1 day preceding the biopsy.
 
An open muscle biopsy will be peformed on one leg at the baseline, and on the other leg at 3 months post gene transfer.
 
																	
	5 Pronbyl	actic prec	Inisolone/pre	dnisone taper begir	ns on Day	/-1 and is	stanered	according	to AST A	T and FI	ISnot resu	lts Antici	nate that	most subia	rts will be d	n nrednisol	one for up to	120 days
				st of the anesthesia					. to AST, AL	. 1, anu EL	Sportesu	its. Antici	pate tridt	most subje	.cs will be (	n preunisolo	me for up to	120 0035.
	7. Day 0 V	ital Signs	Heart rate, re	espiratory rate, puls	se oxime	try, temp	erature, a	nd blood j								nd at least e	very five min	utes during
				minutes post-infusi ontinue at post-trea												f/u visits wil	l be collecter	d at locally
				es include ALT, AST			33, 43, 73	, 3/10 5, 12	., 10, 0110 2		Post Sell	e aunarei	samples	scheduleu		., a visits Wil	. se concelet	actiocally

Note: There will be a flexibility of working days for each of the planned study visits including screening to adjust the schedule to any unanticipated event. The windows for each appointment are as follows:

- ٠
- ٠
- ٠
- Days 7 and  $14 \pm 2$  days Days 30  $\pm$  3 days Days 60 and 90  $\pm$  7 days Day 180, and Months 12, 18 and 24  $\pm$  14 days •

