#### 3.11 Outcome Measures

The intravascular limb infusion for gene therapy (ILI-GT) stage of the study is proposed as a phase I/II clinical trial inclusive of safety and efficacy outcome measures.

- A. Safety is the primary outcome for this clinical gene transfer trial. Stopping criteria are based on development of unacceptable toxicity defined as the occurrence of **two or more** unanticipated Grade III or higher treatment-related toxicities.
- B. Efficacy outcome measures: Muscle biopsy analysis for safety and transgene expression will be studied using multiple serial sections.
  - i. Expression of GALGT2 as demonstrated by immunofluorescent staining with anti-CT epitope antibodies or WFA lectin in muscle biopsy sections
  - ii. GALGT2 protein expression quantified by western blot and assessed by densitometry in muscle biopsy tissue

For each of these measures, statistical analysis based on differences between pre- and post-gene transfer muscle specimens will be analyzed using a paired t test (p < 0.05). Sections and western blots will be prepared by a single technician, who will blind the sample identifier; images will be obtained and expression assessed by another technician blinded to the sample time point.

- C. Exploratory functional outcome measures will be performed on the schedule as described.
  - i. The 6 minute walk test (6MWT), with either stabilization or a statistically significant change in distance walked on the 6MWT at 6 or 12 months after injection to be considered evidence of a positive result.
  - ii. Strength and functional testing will be performed at baseline and at days 90,180, and at months 12, 18 and 24. This will include the 6MWT distance as the primary functional variable. The maximum voluntary isometric contraction testing (MVICT), which will provide the force generated by the muscles of knee extension and knee flexion, will be an exploratory measure, as will the 100 meter walk time and the NSAA.

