#### 3.12 Statistical Analysis

Measure of the 100 meter walk/run and MVICT of lower limb muscles will be analyzed by paired t-tests with a significance level of p = 0.05.

ALL data will be shared with the DSMB as gathered for each study subject. Any adverse events will be fully discussed with the DSMB and reported to the FDA.

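### Paired t-tests at 0.05 do not fit a trial with one subject per dose; the 6MWT success rule is undefined, and an MTD cannot be established from it

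*Combined protocol and SAP*

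**What the plan says.** **Sample size.** The Synopsis, section 2.1 and section 3.5 all give one subject in the low-dose cohort and one in the high-dose cohort, two in total. The high dose is twice the low dose.

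**Tests.** The Synopsis (Statistical Analysis) lists fibre staining, the 6MWT, the 100 m walk/run and MVICT, and says for each that "statistical analysis based on differences between pre- and post-gene transfer examinations will be analyzed using a paired t-test", with p below 0.05 as the criterion. Section 3.11(B) says of the immunofluorescence and western blot measures that differences between "pre- and post-gene transfer muscle specimens will be analyzed using a paired t test (p < 0.05". Section 3.12 adds that the 100 m walk/run and "MVICT of lower limb muscles will be analyzed by paired t-tests with a significance level of p = 0.05". The visible text does not state the unit of analysis, whether the two doses are pooled, or whether the tests are one- or two-sided.

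**Source of the pairs.** Section 2.1 states: "Open muscle biopsy of the quadriceps (in the leg contralateral to the pre-treatment biopsy) will be performed at 90 days post ILI-GT procedure". Section 3.8 repeats this with an exception: "biopsy will be in the contralateral leg to the pre-treatment biopsy, unless otherwise determined by the PI". A note to Table 2 says: "An open muscle biopsy will be peformed on one leg at the baseline, and on the other leg at 3 months post gene transfer". The Synopsis also lists "GALGT2 protein expression quantified by western blot and assessed by densitometry in muscle biopsy tissue at 90 and 180 days post-injection". Section 3.6.1 includes "the maximum voluntary isometric contraction testing (MVICT) of knee extension and knee flexors bilaterally".

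**6MWT rule.** The Synopsis counts either stabilization or a statistically significant change as a positive result, at 90 and 180 days. Section 3.11(C)(i) has the same rule at 6 or 12 months.

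**MTD.** The Synopsis (Sample Size), section 2.1 and section 3.5 each say that the escalation scheme is meant to establish an MTD.

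**The concern.** A paired t-test estimates the spread of the changes from the changes themselves. One change gives no estimate of spread. Two changes give a very poor one, and here they would come from boys on different doses, so any dose-response is counted as noise.

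The secondary biopsy outcomes and the exploratory functional outcomes are therefore tied to a significance criterion that either cannot be evaluated or depends mainly on how alike the two boys happen to be. An analyst who needs a p-value would be pushed towards a unit below the subject, and the result could be read as evidence about patients.

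The 6MWT rule is a separate problem that would remain at any sample size: two readers could classify the same walking data differently. The MTD wording promises a conclusion that two subjects cannot give.

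**Working it through.** The documents contain no power calculation, SD or effect size, so there is no figure of the plan's own to reproduce. Inputs from the documents are n = 1 per dose, n = 2 in total, and alpha 0.05. Two-sided testing is assumed, with one-sided values given for range. All effect sizes and correlations below are assumptions.

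**1. Degrees of freedom, subject as unit.** df = n − 1. Within a dose, df = 1 − 1 = 0: the SD of the changes cannot be estimated, and t and p are undefined. Pooled over doses, df = 2 − 1 = 1, and the critical |t| is 12.706 (one-sided 6.314).

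**2. What significance needs at n = 2.** For changes x1 and x2, t = (x1 + x2)/|x1 − x2|. Significance requires the same sign and a larger-to-smaller ratio of at most (12.706 + 1)/(12.706 − 1) = 1.171. The smaller change must therefore be at least 85.4% of the larger (one-sided 72.7%). Hypothetical gains of 50 m and 100 m give t = 150/50 = 3 and p = (2/π)·arctan(1/3) = 0.20.

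**3. Power at n = 2.** For equal true effects of d SDs in both boys, power comes from the noncentral t with 1 df and noncentrality d√2. For unequal effects it was simulated (4,000,000 pairs, unit noise).

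| True effects (SD of change) | Two-sided power |
|---|---|
| 1 and 1 | 9.3% |
| 2 and 2 | 17.6% |
| 5 and 5 | 42.1% |
| 1 and 2 | 10.4% |
| 2 and 4 | 10.0% |
| 5 and 10 | 0.4% |

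One-sided power for the first three rows is 18.0%, 34.2% and 73.1%. If the effect doubles with the dose, a larger effect eventually lowers the chance of significance, because the difference between the boys enters the denominator.

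**4. A unit below the subject, MVICT as the example.** MVICT can pair each leg with itself. For one muscle group, two boys give 4 changes and 3 df if legs are treated as independent (critical |t| 3.182). Simulated type I error for a test of the population mean change (2,000,000 draws):

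| Assumed within-boy correlation of change | Type I error |
|---|---|
| 0 | 5.0% |
| 0.3 | 8.0% |
| 0.5 | 11.0% |
| 0.9 | 23.2% |

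**5. Biopsies.** By default the baseline and 3-month specimens come from opposite legs. A before/after comparison within one boy therefore contains a leg and site difference as well as any effect of gene transfer.

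**6. 6MWT rule.** Assumed losses of 100 m and 110 m give t = −210/10 = −21 and p = (2/π)·arctan(1/21) = 0.030. Read literally, that is a statistically significant change. On timing, 180 days and 6 months roughly coincide. The conflict is 90 days against 12 months, and both time points in the Synopsis against either one in section 3.11.

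**7. MTD.** With 0 DLTs in 1 subject, the exact one-sided 95% upper limit for the DLT rate is 1 − 0.05 = 95%. At an assumed true rate of 33%, a single subject shows no DLT with probability 1 − 0.33 = 67%.

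**The case against.** The strongest reply is that safety is primary, the tests are secondary or exploratory, and a unit other than the subject may be intended. Parts of this stand.

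- **Other units are computable.** A reader might infer that the walk tests allow no unit but the subject. That goes too far: both are repeated at five visits after baseline, and MVICT covers two muscle groups in each leg, so a within-boy test could be run. It would rest on replicates from one or two boys.
- **Not every within-boy test is invalid.** A reader might infer that any test on legs or fibres exceeds 5%. The rates above concern a population mean. If one boy's legs vary independently about his own mean change, a two-leg test about that boy keeps its level. The plan does not say which inference it wants.
- **Text may be missing.** Section 3.6.1 refers to section 3.8 for the rationale and methods of biopsy site selection, but visible section 3.8 has little of this, and there are gaps there and in section 2.1. The unit or site matching may be specified in removed text, and the investigator may depart from the contralateral default. Statements about biopsy units are therefore conditional, and no error rate for fibres is claimed.
- **Improvement was probably intended.** The 6MWT rule pairs change with stabilization, as a positive result in a progressive disease. The literal reading shows that the wording is incomplete, not that the sponsor would count decline as success.
- **The MTD is a wording point.** No visible rule uses a declared MTD; escalation rests on DLTs and DSMB review.

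None of this supplies degrees of freedom within a dose at the subject level, gives the 6MWT rule a direction, or reconciles its time points.

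**Conclusion.** The concern holds and should be fixed. That the subject-level tests have 0 df within a dose and 1 df pooled follows from the design alone, as does the 1.17 ratio limit once two-sided testing is taken. The power figures rest on assumed effects and normal changes, and the MVICT error rates on assumed correlations; they show scale and are not predictions for this trial. The missing direction and the conflicting time points of the 6MWT rule are plain on the page. The lack of a definition of stabilization is a statement about the visible text only.

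The consequence is confined to the secondary and exploratory efficacy tests and the MTD wording. A reader might infer that the safety assessment or the halting rule is undermined. The documents do not support that: the primary safety description and the rule in sections 4.2 and 4.3 do not use these tests.

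**What to change.** **(a) Synopsis (Statistical Analysis), 3.11(B) and 3.12.** Replace the paired t-tests and the 0.05 criteria with per-subject listings: the baseline value, each follow-up value and the change, shown by dose and not pooled across doses. Show spread across sections, blots, fibres or legs as within-subject variation only. State the leg and muscle of each biopsy beside its result.

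**(b) Synopsis (Secondary Outcomes) and 3.11(C)(i).** Remove the significance-based 6MWT success rule. If a criterion is kept, prespecify its direction, a definition of stabilization and one set of time points, and label it descriptive.

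**(c) Synopsis (Sample Size), 2.1 and 3.5.** Replace the MTD aim with: to describe safety and tolerability in one subject at each of two doses; no MTD will be declared.

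**Cost.** Wording changes only, with no added subjects, visits, biopsies or assays. Under section 6.4 the amendment needs IRB review and approval before it is implemented. What is given up is a set of p-values and an MTD claim that the design cannot support.
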